4.3.4 Rules for safety observations

4.3.4.1 Multiple safety assessments

For tabulations of visit summaries, changes from baseline or shift analyses, if multiple measurements are included within a relative day window, the measurement closest to the target day will be used; in the case of a tie, the measurement obtained on the earlier day will be used in the analyses. In case of ties located on the same side of the target day (i.e., more than 1 value for the same day), the mean of the values will be used.

4.3.4.2 Adverse events at patient level

When a patient has the same adverse event, based on SOC/PT, reported multiple times in a single analysis period, the patient will only be counted once at the SOC/PT level in adverse event frequency tables.

When a patient has the same adverse event, based on preferred terminology, reported multiple times in a single analysis period, the following criteria, in order of precedence, will be used to select the event to be included in summary tables:

1. Relationship to study medication
2. Intensity of event
3. Onset date and time

When assessing relationship to study medication, relationship is reported by the Investigator into 2 categories - related and not related. Related events will take precedence over not related events in determining the event to include in summary tables.

More intense events will take precedence over less intense events in determining the event to include in summary tables.

Earlier onset date-time events will take precedence over late onset date-time events in determining the onset to include in summary tables.

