Adverse events that occur following completion of study termination/early termination procedures should be recorded on the AE page of the eCRF only if the Investigator considers the event as clinically significant and as related to study medication or study procedures. All SAEs that occur within 90 days of administration of the last dose of study medication (regardless of causality) must be reported immediately (Section 6.4.4). Concomitant medications used following study termination procedures should be recorded only if relevant to treatment of patients for events described above.

Variables

The following variables will be collect for each AE:

- AE (verbatim)
- The date when the AE started and stopped
- If AE is of maximum intensity
- Whether the AE is serious or not
- Investigator causality rating against the Investigational Product (yes or no)

- Action taken with regard to investigational product
- AE caused patient's withdrawal from study (yes or no)
- Outcome.

In addition, the following variables will be collected for SAEs:

- Date AE met criteria for serious AE
- Date Investigator became aware of serious AE
- AE is serious due to
- Date of hospitalization
- Date of discharge
- Probable cause of death
- Date of death
- Autopsy performed
- Causality assessment in relation to Study procedure(s)
- Causality assessment in relation to Other medication
- Description of AE.

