4.2.4.1 Adverse event analysis

Adverse events (AE) will be classified in accordance to the Medical Dictionary for Regulatory Activities (MedDRA) dictionary. All adverse events will be coded using the latest available version of MedDRA by the database lock.

Treatment-emergent AEs (TEAE) are defined as AEs occurring after the first dose of study medication through the end of the treatment plus 7 days (or + 90 days for SAEs and other clinically significant or related AEs), including AEs collected after patients initiate glycemic rescue therapy.

AEs occurring after Study Termination but considered by the Investigator as clinically significant and as related to study medication or study procedure, and SAEs occurring within 90 days of the last administration of study medication or EQW if in the extension phase will be recorded on the AE eCRF and reported in the AE listing.

Any AE that is recorded as the reason for study discontinuation will be considered an adverse event leading to discontinuation (DAE) regardless of the date recorded. All DAEs will be reported regardless of when they occurred. Note, any AE that is a DAE under these rules will also count as an AE when reporting.

Off-treatment AEs will be defined for the following:

- Treatment completers to Week 52: An AE that occurs between Week 52 to Week 62 and starts the day after last dose of open-label EQW + 7 days (or + 90 days for SAEs and other clinically significant or related AEs). Only patients completing study medication to Week 52 will be considered. Patients completing study medication to Week 52 but who withdraw prior to Week 62 will also be included.
- Premature discontinuation: An AE that starts the day after last dose of study medication + 7 days (or + 90 days for SAEs and other clinically significant or related AEs), for patients who discontinue study medication before Week 24 or Week 52.

AEs for the combined periods are those that occur during the Treatment period or post-treatment.

AEs with a start date prior to the first administration of study medication will be classified as pre-treatment (non-treatment emergent).

AEs with a stop date prior to the date of the first administration of study medication will be classified as pre-treatment (non-treatment emergent) AEs.

In case of missing AE severity, AE causality, or AE seriousness, a worst-case approach will be used. For AE missing severity, the AE will be considered severe; for missing causality, the

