AE will be considered as possibly-related to study medication; for missing seriousness, the AE will be considered serious.

On-treatment AEs (TEAEs) will be summarized for 24-week controlled assessment period and 28-week extension period as defined below. Off-treatment AEs for treatment completers to Week 52 will be tabulated where required. Off-treatment AEs for patients who prematurely discontinued will be listed only.

An overall summary of number and percentage of patients experiencing at least 1 TEAE will be presented for EQW and PBO. The summary will be presented by study period (controlled assessment period and extension period). A summary of AEs during the Treatment period for patients with actual treatment EQW during the controlled assessment period will be provided. The AE summary will include the number and percentage of patients experiencing any AE, any SAE, any AE related to treatment per Investigator's discretion, any AE leading to treatment discontinuation, any AE leading to study withdrawal, and any fatal AE.

Additionally, all TEAEs will be summarized for each treatment group as follows:

- AEs summarized by SOC, PT, maximum intensity (Mild, Moderate, Severe), causality (Not related, Related), action taken, and outcome.
- SAEs summarized by SOC and PT, maximum intensity (Mild, Moderate, and severe), causality (Not related, Related).
- AEs leading to treatment discontinuation summarized by SOC and PT.
- Frequent AEs (AE with at least 5% incidence in any treatment) summarized by preferred term.
- Non-serious frequent AEs summarized by SOC and PT.
- Potentially immune-related AEs summarized by antibody status (positive versus negative), SOC and PT.
- Potentially immune-related AEs summarized by antibody titer (higher: ≥ 625 versus low: < 625), SOC and PT.
- Potentially immune-related injection site-related AEs summarized by SOC and PT.

Summaries by maximum intensity will be presented separately for the controlled assessment period (Safety analysis set) and extension period (subset of Safety patients who received open-label EQW during the extension period). All other AE summary tables will be presented by study period in a single table.

Potentially immune-related AEs will be identified using the PTs given in [Appendix B4](#).

Injection site-related AEs will be identified using AEs within higher-level term "Injection site reactions".

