4.3.4.3 Adverse event at event level

At event level, each unique AE record will be counted. Unique AE record can be obtained by collapsing all AE records following a standard algorithm described below.

To ensure that multiple events for the same patient are counted accurately in the summaries, a methodology for collapsing AE records and reporting for the analysis will be followed as below. For each patient and PT, AE records will be collapsed into a single record (unique AE) when:

1. Multiple AE records have the same onset date,
2. The onset date of an event record is either the same day or 1 day later than the resolution date of a preceding event record (contiguous events),
3. The onset date of an event record is after the onset date and prior to or on the resolution date of a preceding event record (overlapping events).

The unique AE record will contain the earliest onset date, latest resolution date (if available), highest intensity, relationship (yes/no), and highest action taken in the following order (highest to lowest): drug discontinued, drug interrupted, none. In addition, the unique AE record will be classified as a SAE if at least 1 AE record was classified as a SAE and the unique AE record will be classified as requiring treatment if at least 1 AE record required treatment.

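### The patient-level AE selection rule ranks relatedness above intensity, so the maximum-intensity tables can show less than a patient's maximum

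*SAP*

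**What the plan says.** SAP 4.3.4.2 covers a patient who reports the same preferred term more than once within an analysis period. It states that "the following criteria, in order of precedence, will be used to select the event to be included in summary tables" and lists three: relationship to study medication, intensity, and onset date and time. It then spells out the first: "Related events will take precedence over not related events in determining the event to include in summary tables". Intensity therefore decides only between events tied on relatedness. No summary table is excluded.

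SAP 4.2.4.1 lists the planned displays of treatment-emergent events. Two carry maximum intensity: "AEs summarized by SOC, PT, maximum intensity (Mild, Moderate, Severe), causality (Not related, Related), action taken, and outcome" and "SAEs summarized by SOC and PT, maximum intensity (Mild, Moderate, and severe), causality (Not related, Related". The only further text on these displays concerns layout: "Summaries by maximum intensity will be presented separately for the controlled assessment period (Safety analysis set) and extension period". No separate selection rule is given for them.

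Two neighbouring rules also bear on this. For incomplete records, SAP 4.2.4.1 says "In case of missing AE severity, AE causality, or AE seriousness, a worst-case approach will be used": missing severity becomes severe and missing causality becomes possibly related. SAP 4.3.4.3, on event-level counting, merges records of one term that start on the same date, follow on directly or overlap, and gives the merged record the highest intensity and the "highest action taken in the following order (highest to lowest): drug discontinued, drug interrupted, none".

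**The concern.** A precedence order that puts relatedness first does not return the maximum intensity. It returns the intensity of the most intense related event if there is one, and otherwise that of the most intense not-related event. Whenever the more intense episode is judged not related and a milder one related, a table labelled maximum intensity shows the milder grade.

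Safety and tolerability against placebo is a primary objective (Protocol 2.1, SAP 1.1.1), and these tables are where a reader looks for how severe the events were. The error has one direction: the rule can lower the grade shown but cannot raise it.

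It also sits badly with the worst-case handling of missing data. That rule fills in values and does not choose between events, so there is no formal contradiction. In combination, though, the two can defeat the conservative intent. A not-related event set to severe because its grade is missing would be displaced by a mild related event of the same term. Likewise, a mild event counted as related because its causality is missing would displace a severe not-related one.

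**Working it through.** The plan states no figure to reproduce, so the check applies the written rule to every possible pair of reports.

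**Inputs.** Intensity has three levels (mild = 1, moderate = 2, severe = 3) and causality two (not related = 0, related = 1), both from SAP 4.2.4.1. The precedence order comes from SAP 4.3.4.2.

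**Set-up.** Write each report as (R, I), with R in {0, 1} and I in {1, 2, 3}. That gives 2 × 3 = 6 states per report and 6 × 6 = 36 ordered pairs for two separate reports of one term. The rule picks the report with the larger R and, if R is tied, the larger I. The true maximum intensity is max(I₁, I₂).

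**Same causality.** There are 2 × 3 × 3 = 18 such pairs. R is tied, so intensity decides and the maximum is always shown.

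**Different causality.** There are also 2 × 3 × 3 = 18 of these pairs. The related report is always chosen. Across the 9 intensity combinations, the related report is less intense in 3, tied in 3 and more intense in 3. Counting both orders gives 6, 6 and 6. Only the first group goes wrong:

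| Related report | Not-related report | Shown | True maximum | Ordered pairs |
|---|---|---|---|---|
| Mild | Moderate | Mild | Moderate | 2 |
| Mild | Severe | Mild | Severe | 2 |
| Moderate | Severe | Moderate | Severe | 2 |

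**Result for the rule as written.** Intensity is too low in 6 of 36, too high in 0 and correct in 30. Of the 6, 4 are off by one grade and 2 by two grades. A severe event is hidden in 4, and in 2 of those it appears as mild. Causality is correct in all 36.

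**Alternatives on the same 36 pairs.**

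| Selection | Maximum intensity wrong | Related event hidden |
|---|---|---|
| As written: relatedness, then intensity | 6 | 0 |
| Swapped: intensity, then relatedness | 0 | 6 |
| Each attribute selected separately | 0 | 0 |

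The swap fails on causality in the same 6 pairs, because there the more intense report is the not-related one.

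**Does event-level merging prevent this?** Only in part. SAP 4.3.4.3 keeps the highest intensity for records that share an onset date, are contiguous or overlap. Episodes separated in time are not merged and remain subject to 4.3.4.2. Mild related nausea in week 2 and severe not-related nausea in week 10, for example, would be tabulated as mild.

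**The case against.** The strongest reply is that the table label already supplies the rule. If the display is of maximum intensity, a programmer will take the maximum, and the specific table would override a general tie-break. That may well happen, but only by departing from 4.3.4.2, which selects one event in a stated order and exempts nothing. The SAP does not say which text governs.

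A second reply is that maximum intensity may be an attribute of each AE record, since Protocol 6.4.3 lists among the variables collected for each AE "If AE is of maximum intensity". On that reading the rule picks the event and the table shows that event's own peak. The line is garbled, and it does not turn the patient-level displays in SAP 4.2.4.1 into summaries of a per-record attribute.

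A third reply has some substance. Separate selection is sound for separate margins. If intensity and causality were cross-tabulated, it could produce a severe related entry from a mild related and a severe not-related event, a combination the patient never had. Since 4.2.4.1 treats the maximum-intensity summaries as tables in their own right, this does not undermine the proposal, but any such cross-tabulation should keep one real event.

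The point about scale also stands. The effect needs the same term, patient and period, separate episodes, differing causality, and the related episode being the milder one, in a trial planning about 77 patients. The tables are descriptive, with no test attached.

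**Conclusion.** The concern holds: the rule as written gives a wrong entry in the maximum-intensity tables whenever a milder related episode accompanies a more intense not-related one. In logical patterns this is 6 of 36, all downwards. The count weights patterns equally and does not estimate how many patients are affected; that frequency cannot be derived from the documents and is probably small.

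The damage is contained. Counts of patients with any AE, any SAE, a related AE or an AE leading to discontinuation do not change. All AEs are still listed, and SAEs and events leading to discontinuation of study medication get their own key-information tables. The efficacy analyses are untouched. The conclusion assumes that 4.3.4.2 is programmed as worded and that the intensity tables are meant to show each patient's highest grade. The correction should be made, given the primary safety objective and the small effort involved.

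**What to change.** Amend SAP 4.3.4.2 to select each attribute separately for a given patient, preferred term and period:

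1. Maximum-intensity tables use the highest intensity reported, regardless of relatedness.
2. Causality tables use related over not related.
3. Action-taken tables use the highest action, in the order already set out in 4.3.4.3.

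If any table crosses intensity with causality, say so and keep one actual event per patient and term in that table. Do not simply exchange the first two criteria.

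The cost is a few lines of SAP text and programming. No new data are needed, since intensity and causality are already assessed for each AE (Protocol 6.4.3).

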4.3.4.3 Adverse event at event level

At event level, each unique AE record will be counted. Unique AE record can be obtained by collapsing all AE records following a standard algorithm described below.

To ensure that multiple events for the same patient are counted accurately in the summaries, a methodology for collapsing AE records and reporting for the analysis will be followed as below. For each patient and PT, AE records will be collapsed into a single record (unique AE) when:

1. Multiple AE records have the same onset date,
2. The onset date of an event record is either the same day or 1 day later than the resolution date of a preceding event record (contiguous events),
3. The onset date of an event record is after the onset date and prior to or on the resolution date of a preceding event record (overlapping events).

The unique AE record will contain the earliest onset date, latest resolution date (if available), highest intensity, relationship (yes/no), and highest action taken in the following order (highest to lowest): drug discontinued, drug interrupted, none. In addition, the unique AE record will be classified as a SAE if at least 1 AE record was classified as a SAE and the unique AE record will be classified as requiring treatment if at least 1 AE record required treatment.

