3.6.5.2 Safety and concomitant medications

Adverse events, hypoglycemic events and concomitant medications on the date of first dose of open-label EQW (Week 24 visit) will be assigned to the extension period as this is considered a conservative approach. Other safety assessments at the Week 24 visit will be considered to have been carried out pre-dose and will therefore be assigned to the controlled assessment period. This is reflected in the definitions below.

Controlled assessment period:

- For patients who do not enter the extension period, the controlled assessment period will be defined as date of first dose of randomized study medication to date of last dose of randomized study medication + 7 days (or + 90 days after last dose of study medication for reporting of serious adverse events (SAEs) and other clinically significant or related AEs).
- For patients who go on to enter the extension period, the controlled assessment period for all safety parameters except AEs, hypoglycemic events and concomitant medications will be defined as date of first dose of randomized study medication to date of first dose of open-label EQW. For AEs, hypoglycemic events and concomitant medications, the controlled assessment period will be defined as date of first dose of randomized study medication to date of the first dose of open-label EQW – 1 day, in order for AEs, hypoglycemic events and medications recorded on the date of first dose of open-label EQW to be assigned to the extension period.

Extension period: For all safety parameters, except AEs, hypoglycemic events and concomitant medications, the extension period will be defined as date of first dose of open-

label EQW + 1 to date of last dose of open-label EQW + 7 days. For AEs, hypoglycemic events and concomitant medications, the extension period will be defined as date of first dose of open-label EQW to date of last dose of open-label EQW + 7 days (or + 90 days for SAEs and other clinically significant or related AEs). The extension period will only be defined for patients who enter the extension period and receive at least one dose of open-label EQW.

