Tables of key patient information for SAEs and AEs leading to discontinuation of study medication will be provided. Adverse events will be listed.

The number of AEs and number of SAEs will be summarized for the controlled assessment period and extension period.

The denominator for summaries will be the number of patients included in the analysis set by treatment group and total. Where the controlled assessment period and extension period are presented side-by-side in the same summary, the denominator for the controlled assessment period will be the number of patients in the Safety analysis set by treatment group and total; the denominator for the extension period will be the number of patients in the subset of Safety patients who received open-label EQW during the extension period by treatment group and total.

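### The event-level AE collapsing rule has no break at the first open-label EQW dose, so an AE that starts on EQW can leave the extension count and carry its SAE flag into the controlled period

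*SAP*

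**What the plan says.** SAP 4.3.4.3 defines a unique AE for event-level counting: "For each patient and PT, AE records will be collapsed into a single record (unique AE) when" any of three conditions is met. The first is a shared onset date. The second is contiguity: "The onset date of an event record is either the same day or 1 day later than the resolution date of a preceding event record". The third is overlap: "The onset date of an event record is after the onset date and prior to or on the resolution date of a preceding event record". None refers to study period or treatment.

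The merged record is built as follows: "The unique AE record will contain the earliest onset date, latest resolution date (if available), highest intensity, relationship (yes/no), and highest action taken". For seriousness, "the unique AE record will be classified as a SAE if at least 1 AE record was classified as a SAE".

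The neighbouring patient-level rule, SAP 4.3.4.2, is limited by period: for the same event "reported multiple times in a single analysis period, the patient will only be counted once at the SOC/PT level in adverse event frequency tables".

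SAP 3.6.5.2 ends the controlled period for AEs on the day before the first open-label EQW dose, for patients who enter the extension. AEs dated on the day of that dose "will be assigned to the extension period as this is considered a conservative approach". SAP 4.2.4.1 classifies pre-treatment AEs by start date and promises event counts by period: "The number of AEs and number of SAEs will be summarized for the controlled assessment period and extension period".

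**The concern.** Group B receives placebo to Week 24 and EQW from then on, so for these patients the period boundary is also a change of drug. A rule that keeps the earliest onset and the worst attributes, with no break at that boundary, can carry the seriousness of an EQW-onset record back to a placebo-period date. That runs against the SAP's own choice to give switch-date AEs to EQW as the conservative option.

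The output at stake is the by-period count of AEs and SAEs, which serves the primary safety objective. The placebo arm is small, about 77 × 2/7 = 22 patients, so a single SAE in the wrong column would be noticed.

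The protocol (section 12.6.7.1) left detailed classification of extension-period on-treatment AEs to the SAP. The SAP gives no rule for a same-term event that worsens after the switch.

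**Working it through.** The plan gives no figure for this rule, so there is none to reproduce. The check applies the three conditions literally to one placebo patient.

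**Inputs assumed for illustration**
- Day 1 is the first randomized dose. The first open-label EQW dose is on Day 1 + 24 × 7 = Day 169.
- Record A: Days 160 to 175, mild, not serious, no action.
- Record B: same preferred term, severe, serious, drug discontinued, ending Day 185. Its start day is varied.
- Period assignment: onset before Day 169 is controlled; onset on or after Day 169 is extension.

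**Does B merge with A?**
- B starts Day 172: 160 < 172 ≤ 175, so the records overlap and merge.
- B starts Day 176: 176 = 175 + 1, so they are contiguous and merge.
- B starts Day 177: 177 = 175 + 2, so no condition is met and they stay separate.

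**Resulting event counts**

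| Case | Controlled (placebo): AE / SAE | Extension (EQW): AE / SAE |
|---|---|---|
| Records not collapsed, any B start above | 1 / 0 | 1 / 1 |
| Rule as written, B starts Day 172 or 176 | 1 / 1 | 0 / 0 |
| Rule as written, B starts Day 177 | 1 / 0 | 1 / 1 |
| Break at first EQW dose, B starts Day 172 or 176 | 1 / 0 | 1 / 1 |

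Under the rule as written, the merged record also carries B's severe grade and drug discontinuation with a Day 160 onset.

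**Change per merge (rule as written minus break)**
- Controlled AE: 1 − 1 = 0.
- Extension AE: 0 − 1 = −1.
- Controlled SAE: 1 − 0 = +1, when B is serious and A is not.
- Extension SAE: 0 − 1 = −1, when B is serious.

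For an EQW patient the arithmetic is the same, but both periods are EQW. The flag moves to the wrong period and stays with the right drug.

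**Recurrent events (hypothetical).** Take weekly onsets on Days 1, 8, …, 358, which is 24 records before Day 169 and 28 from Day 169 on. If each resolves 6 or more days after onset, every record touches the next and all 52 chain together, giving 1 controlled and 0 extension events. Collapsing within period gives 1 and 1. If each resolves 5 or fewer days after onset, nothing merges and the counts are 24 and 28.

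**A single record.** If the site keeps one record from Day 160 to Day 185 and updates it to severe and serious, the count is controlled 1 AE and 1 SAE, with or without the break. Nothing is collapsed, so the break changes nothing.

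**The case against.** **The mechanism is inferred.** No sentence says that collapsing precedes period assignment, or that a merged record's period follows its earliest onset. Collapsing inside each period's table is also compatible with the text. This stands as a limit on certainty. Even so, 4.3.4.3 states its scope as patient and preferred term, 4.3.4.2 states a period limit, and 4.2.4.1 uses start date for pre-treatment status, so the literal reading is the natural one.

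**A reader might infer bias in favour of EQW.** The documents do not support that. The rule also pulls extension SAE flags into the controlled-period EQW column. With about 77 × 5/7 = 55 EQW patients against 22 on placebo, more patients on EQW could have straddling records. The net effect could go either way.

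**A reader might infer that placebo gains an extra AE.** It does not; the earlier record was already counted there.

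**A reader might infer that the severity and incidence tables are wrong.** The event counts promised in 4.2.4.1 are of AEs and SAEs, not of grades. Patient-level tables follow 4.3.4.2 and are already limited to one period, unless they are built from collapsed records. The SAP does not say which. Injection-site reactions are summarized as patients by visit, with windows split at the switch (Table 3.6).

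**A reader might infer that Appendix B1 widens the effect.** Partial end dates are imputed late, to the end of the month or year, which could create overlaps. A completely missing end date for a resolved event that began after first dose is set to its onset, which shortens the span. Nothing states that imputed dates enter the collapse, so no net direction follows.

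**The trigger is narrow.** It needs two same-term records that meet across one date, and the SAE shift needs the later one to be serious. Listings and the key-information tables for SAEs would expose a case. This limits the practical weight of the point, but the counting rule still needs correcting.

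**Conclusion.** The point holds for the event-level counts of AEs and SAEs by period. As written, and assuming assignment by earliest onset, the rule gives a wrong by-period count whenever same-term records meet across the first open-label EQW dose. In placebo patients it can place an EQW-onset SAE under placebo.

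The size is known only per merge, as shown above. The documents give no AE rates, so frequency cannot be estimated, and the net direction in the EQW–placebo comparison cannot be determined. An effect on patient-level tables is not established.

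**What to change.** Add to SAP 4.3.4.3: *Records are collapsed only within the same study period as defined for AEs in Section 3.6.5.2. A record with onset on or after the first open-label EQW dose is not merged with an earlier-onset record. Intensity, relationship, seriousness and action are taken only from records in that period.*

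Also state that patient-level tables apply 4.3.4.2 within period, and whether they draw on raw or collapsed records.

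The cost is a short SAP insertion and one additional BY variable in the collapsing program. The downside is that a continuing event recorded twice across Week 24 counts once in each period, which suits by-period reporting and matches 4.3.4.2. The change does not cover a single site record that worsens after the switch; that case needs its own rule if the sponsor wants the worsening attributed to the extension.
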